Together, these findings suggest that remote therapy and thus assessment can be safely and feasibly applied. The use of audio/video communication will be piloted and used should the pilot show that this can be done safely and feasibly. For the Turkey site, audio/video assessments may be used for both screening and assessments).

Methods of assessment will be recorded, and if necessary, accounted for in the analyses. See Appendix 8 for copies of all screening and outcome measures.

Version 4.1 11 March 2019 12

-

¹ Richards, D. and Viganó, N. (2013), Online Counseling: A Narrative and Critical Review of the Literature. J. Clin. Psychol., 69: 994–1011. doi:10.1002/jclp.21974

² Knaevelsrud C, Brand J, Lange A, Ruwaard J, Wagner B. Web-Based Psychotherapy for Posttraumatic Stress Disorder in War-Traumatized Arab Patients: Randomized Controlled Trial J Med Internet Res 2015;17(3):e71

At baseline, socio-demographic data including sex, age, country of origin, education, religion, marital status and work status will be collected using an ad-hoc form developed specifically for RE-DEFINE. The form will also collect information on education, housing, employment opportunities in Turkey (as measures to improve social integration). Information on the adverse life events and environmental stressors will be collected using the Harvard Trauma Questionnaire Part A (HTQ) (30) and the Post-Migration Living Difficulties (PMLD) and the Recovery Environment (31). We will administer the HTQ Part A (30), in which respondents are asked whether they have experienced each of the events, and a 17-item Checklist for Post-Migration Living Difficulties (PMLD) (31).

In addition, the following assessment scales will be administered (as reported in Table 1 below and Appendix 7 assessment schedule):

- 1. baseline: ad-hoc recruitment form, WHODAS 2.0, PHQ-9, WHO-5 Wellbeing index, PSYCHLOPS, HTQ Part A, PCL-5, EQ-5D-3L, and CSSRI-EU (adapted);
- 2. post-intervention: GHQ-12, M.I.N.I., WHODAS 2.0, PHQ-9, WHO-5 Wellbeing index, PSYCHLOPS, PMLD, and PCL-5;
- 3. 6-month follow-up: GHQ-12, M.I.N.I., WHODAS 2.0, PHQ-9, WHO-5 Wellbeing index, PSYCHLOPS, PMLD, PCL-5, EQ-5D-3L, and CSSRI-EU (adapted);
- 4. 12-month follow up: GHQ-12, M.I.N.I., WHODAS 2.0, PHQ-9, WHO-5 Wellbeing index, PSYCHLOPS, PMLD, PCL-5, EQ-5D-3L, and CSSRI-EU (adapted).

Table 1 Overview of measures that will be administered during the study

Concept	Screening	Baseline	Post- intervention	6-month follow-up	12-month follow-up

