The HTQ, developed by Mollica and colleagues is a self-report questionnaire with 4 parts. The purpose of part 1/A is to measure traumatic life events.

The PMLD checklist was used to assess the levels of stress due to typical post-migration stressors developed from discussions with immigrant and refugee communities in Sydney. The checklist asks respondents to rate their experience of the problems, during the last 12 months, on a five point scale ('was not a problem' to 'a very serious problem'). A high cumulative score indicates a high degree of post-migration stressors.

Randomization

Randomization will occur at individual level and will be stratified by recruiting centre. Randomization will be centralized and coordinated by the WHO Collaborating Centre (CC) of the University of Verona. Eligible participants will be randomly assigned to one of the two groups with an equal probability of assignment to each group (allocation ratio 1:1). The randomization schedule will be generated using the web-based software Castor Electronic Data Capture (47). This electronic tool employs a variable block randomization method, in order to allocate groups randomly permuted in blocks of unequal size. The site investigator will not know the block size. Members of the research team involved in the recruitment will be able to access the web-based software to randomize each new enrolled participant, but will not be able to access the randomization list. In addition, the web-based software will allow random allocation only after the main information on the enrolled participant is entered, upon verification of the inclusion criteria. After random allocation, the software will produce a unique identification number (ID) for each participant. Recruiting members of the research team will be able to access the web-based software to randomize each new enrolled participant and will be immediately informed about the allocation arm, but will not be able to access the randomization list. The randomization list will be accessible only to the data manager.

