On the basis of data extrapolated from prevention trials, it is expected an event rate (psychiatric diagnosis) of around 15% at six months (primary outcome) (48;49). However, these prevention trials were conducted in unselected populations that were not exposed to migration stressors. By contrast, refugees are exposed to pre-migration, migration and post-migration chronic stressors that are associated with up to ten times increased rates of mental disorders (50). On these grounds, we anticipate an incidence rate of mental disorders of 25% at six months in this population. It is hypothesized that the provision of the SH+ programme will show a clinically significant advantage by producing a between groups absolute difference of 10%. A sample size of 500 participants (250 in each group), achieves 80% power for a 0.05 level of significance between the two proportions of people diagnosed with mental disorders at six months. Assuming that a relevant proportion of refugees might be lost at study endpoint (due to the specific characteristics of this population), the final sample size will be of 600 participants (300 in each group). All trial phases will be piloted before the fully powered randomized trial with approximately 3-4 refugees in order to check and harmonise all procedures.

Characteristics of the experimental intervention

The Self Help Plus (SH+) programme

SH+ programme has been developed by WHO and collaborators working in the humanitarian field, with expertise in global mental health and psychosocial interventions. SH+ programme consists of a pre-recorded audio course, complemented with bibliotherapy, and thanks to this format not requiring much time from experts for implementation. The potential of using a psychoeducational course to access hard-to-reach populations has been demonstrated previously (51). Evidence for bibliotherapy is also promising (52). Furthermore, research has found that guided self-help programs produce much better results than "pure" (unguided) self-help, and the effects produced by guided self-help are surprisingly similar to face-to-face psychological treatment (53). SH+ was designed to be relevant for large segments of adversity-affected populations: it is intended to be transdiagnostic, easily adaptable to different cultures and languages, and both meaningful and safe for people with and without mental disorders. WHO organized extensive peer-review, with 43 international experts reviewing the intervention.

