The statistical analysis will be masked. The trial statistician will be blinded to the treatment groups until the analysis has been completed. Moreover, the trial statistician will not be involved in determining participants' eligibility, in administering the intervention, in measuring the outcomes, or in entering data (data will be entered with a double-entry procedure). All analyses will be performed using Stata/SE, Release 14.2.

Two data locks will occur during the study. The first one will happen 6 months after the end of the 12-month enrolment period (month 18 from study beginning), when the information on the primary outcome and on the short-term secondary outcomes will be available for all study participants. The second one will happen at the end of the study (month 24 from study beginning), when information on the long-term secondary outcomes will be available for all participants.

All primary and secondary analyses will be performed on an intention-to-treat (ITT) basis. The ITT population will consist of all participants randomly assigned to the competitive intervention strategies. In order to check the robustness of results, the primary outcome will be additionally analysed using a per protocol (PP) approach, that will include only participants who fulfil the protocol in terms of eligibility, interventions, outcomes assessment at follow-

ups. The analysis of the PP population will be used for confirmatory purposes only. If less than 5% of participants does not receive the allocated intervention according to the study protocol, the PP analysis will not be performed.

All analyses reaching statistical significance will be replicated for each recruiting centre and for each population group separately. In addition, all analyses reaching statistical significance will be stratified by methods of assessment (face to face versus telephone or secure online audio/video communication).

Analysis of the primary outcome

The proportion of participants with a psychiatric diagnosis at 6-months follow-up will be compared between the two groups through the chi-square test (primary analysis). A multivariate analysis (secondary analysis) will be performed through a Poisson regression model, with a robust error variance (57), to estimate relative risks directly and to explore the potential confounding effect of prognostic factors, and the interactions with treatment.

Analysis of the secondary outcomes

Secondary outcomes are:

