- GHQ-12 post-intervention, at 6- and 12-months follow-up;
- Proportion of participants with a psychiatric diagnosis (M.I.N.I.) post-intervention and at 12 months of follow-up;
- WHODAS 2.0 post-intervention, at 6- and 12-months follow-up;
- PHQ-9 post-intervention, at 6 and 12 months of follow-up;
- WHO-5 Wellbeing index post-intervention, at 6 and 12 months of follow-up;
- PSYCHLOPS post-intervention, at 6 and 12 months of follow-up;
- EQ-5D-3L: at 6 and 12 months of follow-up;
- PCL-5 post-intervention, at 6 and 12 months of follow-up;
- CSSRI-EU (adapted) at 6 and 12 months of follow-up;
- Proportion of participants leaving the study early (dropouts).

Proportion of participants with a psychiatric diagnosis (M.I.N.I.) post-intervention and at 12 months of follow-up

The proportion of participants with a diagnosis of any mental disorder post-intervention and at 12-months of follow-up will be compared between the two groups through the chi-square test. A multivariate analysis will be performed through a Poisson regression model, with a robust error variance, to estimate relative risks directly and to explore the potential confounding effect of prognostic factors, and the interactions with treatment (57).

GHQ-12, WHODAS 2.0, PHQ-9, WHO-5 Wellbeing index, PSYCHLOPS, PCL-5 post-intervention, at 6- and 12- months of follow-up

For each questionnaire, in case of missing items, the Corrected Item Mean Substitution method (58), will be used (i.e. the item mean across participants weighted by the subject's mean of completed items), using information from subjects belonging to the same treatment arm for the same follow-up time.

The hypothesis that the experimental intervention has no effect on GHQ-12, WHODAS 2.0, PHQ-9, WHO-5 Wellbeing index, PSYCHLOPS, PCL-5 scores will be tested by performing seemingly unrelated regression (59), for each follow-up, controlling for baseline values. In case of joint statistical significance of the coefficients related to treatment status, the effect of treatment on each score will be evaluated through appropriate statistical methods for repeated measurements.

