After the last data lock, a mixed analysis of covariance (ANCOVA) will be performed for each scale, using the values at post-intervention, and at 6- and 12- months of follow-up, controlling for the value at baseline. In case of joint statistical significance of the coefficients related to treatment status, the analysis for each outcome/time combination will be repeated using the last observation carried forward (LOCF) approach: ratings will be carried forward from the last available assessment to the 12-month follow-up assessment. Multivariate analyses will be performed for each scale to take confounding factors into account, again including the baseline value as a covariate.

Proportion of participants leaving the study early (dropouts)

The proportion of participants leaving the study early will be compared between the two groups through the chi-square test (or the Fisher exact test, where appropriate). A multivariate analysis will be performed through a Poisson regression model, with a robust error variance, to estimate relative risks directly and to explore the potential confounding effect of prognostic factors, and the interactions with treatment (57).

Cost-effectiveness analysis (CSSRI)

Overall incremental cost-effectiveness analyses (ICEA) will be conducted from the UK health and social care system perspective and from the UK societal perspective by means of the netbenefit approach (Glick, 2010). Direct costs including formal medical and psychiatric health care (inpatient care, outpatient care, staff, equipment, drugs; formal psychological), psychosocial care (psychological counselling, psychotherapy, social worker, community nurse, sheltered accommodation, day centre, occupational services), legal services (police and court contacts, arrests, legal guardianship), informal services (care provided by relatives or volunteers) will be used for ICEA from the health and social care system (payer) perspective and total (direct costs + productivity losses) will be used for ICEA from the societal perspective.

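### The primary chi-square test uses neither the randomisation stratum (recruiting centre) nor a severity score already collected, so precision available at almost no cost is left unused

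*Protocol*

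**What the plan says.** Under Analysis of the primary outcome, the proportion diagnosed by M.I.N.I. at six months "will be compared between the two groups through the chi-square test (primary analysis"). No covariate or stratum is named. A Poisson model with robust variance follows as a secondary analysis, intended "to estimate relative risks directly and to explore the potential confounding effect of prognostic factors, and the interactions with treatment". Its covariates are not listed.

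The Randomization section states: "Randomization will occur at individual level and will be stratified by recruiting centre". In the analysis text, centre appears only under General approach: "All analyses reaching statistical significance will be replicated for each recruiting centre". That is replication of significant results within centres, not adjustment.

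Severity is measured before allocation. GHQ-12 is taken at screening (Screening phase; Table 1). Under Trial phase assessment, the list for the next visit starts "baseline: ad-hoc recruitment form, WHODAS 2.0, PHQ-9" and also includes PCL-5.

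For the scale outcomes, the seemingly unrelated regression is run "for each follow-up, controlling for baseline values", and the later multivariate models are fitted "again including the baseline value as a covariate".

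The sample-size section states: "A sample size of 500 participants (250 in each group), achieves 80% power for a 0.05 level of significance between the two proportions". The expected rates are 25% and, with a 10-point absolute difference, 15%.

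**The concern.** The confirmatory result rests on the analysis that makes least use of what the trial collects. When the outcome varies between centres and allocation is balanced within them, a test that ignores centre is slightly conservative. When a baseline score predicts the outcome, leaving it out loses precision.

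The secondary Poisson model does not make up for this. It is not the confirmatory test, its covariates are open, and it combines estimation with a search for confounders and interactions.

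At stake is a few points of power in a trial sized for exactly 80%, with 100 of the 600 participants already set aside for loss to follow-up.

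**Working it through.** **1. The Protocol's own figure.** Inputs (Sample size and power calculations): p1 = 0.25, p2 = 0.15, alpha 0.05, power 0.80. Sidedness is not stated; a two-sided test reproduces the figure. The mean proportion is 0.20.

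n per arm = [1.960 × √(2 × 0.20 × 0.80) + 0.842 × √(0.25 × 0.75 + 0.15 × 0.85)]² / 0.10²
= [1.960 × 0.5657 + 0.842 × 0.5612]² / 0.01 = [1.109 + 0.472]² / 0.01 ≈ 250.

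Power at 250 per arm is 0.800. The stated size is right for the unadjusted test.

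**2. Assumed inputs.** The Protocol gives neither the spread between centres nor how well any score predicts a six-month diagnosis. The number of centres is also not stated; the Setting section allows recruitment through one or more organisations. All three are therefore assumptions, varied over a range.

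**3. Simulation.** 500 analysed, 1:1 within centre, marginal risks calibrated to 25% v 15% (20% v 20% under the null), 20,000 trials per scenario. The tests compared were the Pearson chi-square, Cochran-Mantel-Haenszel (CMH) without continuity correction, and modified Poisson with sandwich variance. The Monte Carlo SE of the paired power difference is at most 0.23 points.

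*(a) One centre, one severity score, Poisson v chi-square*

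| Log-odds per SD | AUC | Change in power (points) |
|---|---|---|
| 0 | 0.50 | -0.6 |
| 0.3 | 0.58 | +0.2 |
| 0.5 | 0.63 | +0.9 |
| 0.8 | 0.70 | +2.8 |
| 1.2 | 0.78 | +5.6 |

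For example, power goes from 0.804 to 0.798 with a useless score and from 0.807 to 0.834 at log-odds 0.8.

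*(b) Centre only, six equal centres, CMH v chi-square*

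| Centre SD (logit) | Gain (points) | Chi-square type I error |
|---|---|---|
| 0.3 | 0.3 | 0.048 |
| 0.6 | 1.4 | 0.045 |
| 0.9 | 3.0 | 0.037 |

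An SD of 0.9 is extreme: centre risks of about 8% to 33% at ±1 SD. An analytic check of the type I error gave 0.048, 0.044 and 0.038.

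*(c) Centre and score, six centres, Poisson v chi-square*

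| Centre SD | Log-odds per SD | Gain (points) |
|---|---|---|
| 0.3 | 0.5 | +1.5 (0.806 to 0.821) |
| 0.6 | 0.8 | +3.7 (0.812 to 0.849) |
| 0.6 | 1.2 | +6.2 |

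*(d) Twelve unequal centres* of 4 to 120 people, those under 20 pooled, SD 0.3, log-odds 0.5 (10,000 trials): +1.5 points, adjusted type I error 0.048.

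Across all scenarios the adjusted Poisson test had type I error 0.048 to 0.051.

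**4. What the gains are worth.** From step 1, power at n per arm = Φ[(0.10√n - 1.109) / 0.5612].
- n = 256: Φ(0.875) = 0.81, so 1 point is worth about 6 more analysed per arm.
- n = 270: Φ(0.952) = 0.83, so 3 points are worth about 20 more.
- n = 294: Φ(1.080) = 0.86, so 6 points are worth about 44 more.

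**5. A different model.** A separate simulation (4,000 trials per scenario, five centres, centre SD 0.3) used logistic regression with centre and score. Power rose from 81.1% to 83.0% at an odds ratio of 1.65 per SD, and from 80.4% to 87.8% at 3.3. CMH alone added 0 to 1 point. In the same work the standardised risk difference rejected in 5.4% to 5.9% of null trials (Monte Carlo SE about 0.35 points). A further run of 4,000 trials per scenario put it at 4.8% to 5.7%.

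**The case against.** The strongest reply is that nothing here is wrong. The chi-square is valid, it is the test for which the trial was sized, and an adjusted relative risk is already planned as secondary. The gain rests on assumed prognostic strength. Entry requires GHQ-12 of 3 or more and no M.I.N.I. disorder, which narrows the severity range from both ends and may weaken any score, above all GHQ-12 itself. At log-odds 0.3 to 0.5 the gain is only +0.2 to +1.5 points, and with a useless score it is slightly negative. Centre adds little and drops out if there is one centre. The comparison with the scale outcomes is also loose: each scale has its own baseline value, whereas everyone is free of diagnosis at entry.

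Most of this stands, and it limits the size of the point. It does not remove it. The Protocol fixes which analysis is primary, so a later plan could not move to an adjusted primary test without amending this paragraph. The secondary model, with open covariates and interactions, cannot take the place of the confirmatory test. The loss if the score proves useless is about half a point, while moderate prediction gains 1 to 4 points. The contrast with the scale outcomes is context only; the argument does not depend on it.

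**Conclusion.** The point holds as a nearly free improvement, not as a correction of an error. With moderate inputs (log-odds 0.5 to 0.8 per SD, centre SD 0 to 0.6), adjustment adds about 1 to 4 power points at the same sample size. Gains near 6 points need a strongly predictive score (log-odds 1.2, AUC 0.78). If the score predicts nothing, about 0.6 points are lost. Most of the larger gains come from severity; the main reason to include centre is that the analysis should reflect the randomisation. These sizes are conditional on prognostic inputs that the Protocol does not supply. The adjusted Poisson test kept its nominal type I error. The standardised risk difference may be slightly liberal.

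**What to change.** In Analysis of the primary outcome, make the robust-variance Poisson model the primary analysis:

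- Include treatment, recruiting centre and one pre-named baseline severity score (for example PHQ-9 or GHQ-12), with no treatment interactions.
- Pool small centres by a rule stated in advance, and omit centre if there is only one.
- Take the primary test from the treatment term. Report the adjusted risk ratio and the marginal risk difference with 95% CI; the latter keeps the effect measure used for the sample size. A small-sample variance correction for the risk difference would be prudent.
- Keep the crude chi-square as supportive, and examine interactions separately.

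At minimum, replace the chi-square with a Cochran-Mantel-Haenszel test stratified by centre, accepting that this recovers little of the gain.

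The cost is one paragraph of text, with no new data and no change in sample size. The score and the pooling rule must be fixed before the first data lock.

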total costs (C) per patient (NMB_i = QALY_i*MWTP-C_i) for a MWTP range between UK£ 0 and 50,000 in increments of UK£ 5,000 (Hoch et al., 2002). Incremental NMB will be computed by regressing the NMB on study group (Hoch, Briggs, & Willan, 2002). Results of ICEA will be interpreted according to UK MWTP thresholds recommended by the NICE (Appleby, 2016) and alternatively by country specific thresholds provided by (Woods, Revill, Sculpher, & Claxton, 2016).

Interim analyses

No interim analysis is planned for this trial.

Individual Participant Data meta-analysis

Anonymized Individual Participant Data (IPD) from this study will be re-analysed in an IPD meta-analysis collecting IPD from all available trials on SH+. An ad-hoc protocol for the IPD meta-analysis will be developed.

This secondary analysis of data (IPD meta-analysis) will be mentioned in the informed consent form for participants.

QUALITY ASSURANCE

Participants in the study may directly benefit from their participation in the SH+ intervention, which is based on AMBT techniques that are empirically supported. Their participation will furthermore inform adaptation of the SH+ manual into multiple languages, and thus improve knowledge about delivering mental health interventions in the study areas. Since SH+ is non-pharmacological and there is a broad evidence base for its use, it is unlikely that adverse effects due to the intervention will occur. Adverse events will be responded to as described above. The EAB will play a key role in monitoring adherence to the trial protocol and ensuring research quality as well as prompt and accurate reporting of adverse events.

EXPECTED OUTCOMES OF THE STUDY

The expected outcomes are a reduction in the incidence of psychiatric diagnoses at 6-month follow-up, and a general improvement in mental health symptoms, psychological functioning, well-being, and economic outcomes at each assessment, in refugees in the SH+ intervention arm, as compared to ETAU.

DISSEMINATION OF RESULTS AND PUBLICATION POLICY

A detailed dissemination and communication plan will be developed by WHO in collaboration with project partners. The plan will be circulated across the study sites for comments and final approval.

Local Community

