- Benefits in terms of psychological symptoms and functioning, quality of relationships, and solutions of specific problems both related and unrelated to their traumatic experiences, breaking of unhealthy patterns, and a significant reduction in feelings of distress.
- Contributing to a research that may limit the incidence of newly diagnosed psychiatric disorders in refugees resettled in Turkey.

Potential risks

- There are no guarantees of what participants will experience, and of the duration of changes. For example, it could be that benefits won't last for long periods;
- Based on data from randomized controlled trials already testing the SH+ we are not expecting the intervention worsening mental health condition of participants. However, it could be that participants will experience a transient increase of their mental health problems. In order to mitigate these risks, follow-up assessments and networking with NGOs have been planned to closely monitor the psychological status of participants. In addition facilitators will be trained in basic helping skills and identification of serious adverse events (e.g. imminent risk of suicide) which will further aid identification of any adverse reactions to SH+. Facilitators will be regularly supervised by mental health professionals to further address this risk;
- Participants will not be able to choose in which study arm they will be allocated;
- Participants might experience uncomfortable feelings like sadness, guilt, anger, frustration, and loneliness. Approaching feelings that participants have tried to avoid for a short or long period of time may be painful;
- The participant burden related to the involvement in this study may compete with ongoing responsibilities faced by newly re-settled people (i.e., housing, language issues, new medical system, etc.). This issue has been considered when planning study timeline and assessments. The study is pragmatic and participation implies only 4 assessments of 1 hour each. However, it will be taken into careful consideration throughout the course of the study;
- Participants might feel uncomfortable in a group setting.

INFORMED CONSENT FORMS

Three informed consent forms specific to Turkey have been prepared and attached:

- 1) one for screening (for the pilot or trial phase) (Appendix 3)
- 2) one for participation in the trial phase RCT (Appendix 4)
- 3) one for participation in the pilot (Appendix 5, with differences from Appendix 4 highlighted in green).

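### Secondary symptom scales: the only method named for missed assessments is LOCF to 12 months, run only after a significant joint test, and it is a poor check of robustness

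*Protocol*

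**What the plan says.** All of this is in the Protocol, mostly under Statistical Analysis, Analysis of the secondary outcomes.

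- **Missing items.** Gaps within a questionnaire are filled by corrected item mean substitution. This does not deal with a whole assessment that was missed.
- **First test.** The six scales (GHQ-12, WHODAS 2.0, PHQ-9, WHO-5, PSYCHLOPS, PCL-5) are tested together by "seemingly unrelated regression (59), for each follow-up, controlling for baseline values". The text continues: "In case of joint statistical significance of the coefficients related to treatment status, the effect of treatment on each score will be evaluated".
- **Longitudinal model.** After the last data lock, "a mixed analysis of covariance (ANCOVA) will be performed for each scale" on the three post-baseline values, with baseline as covariate. No condition is attached to it.
- **Missed assessments.** Under a condition worded like the one for the first test, "the analysis for each outcome/time combination will be repeated using the last observation carried forward (LOCF) approach"; and "ratings will be carried forward from the last available assessment to the 12-month follow-up assessment".
- **Other analyses.** Covariate-adjusted models follow for each scale, and dropout is compared between arms.

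Three other sections bear on the point. Sample size and power calculations raises 500 to 600 participants: "Assuming that a relevant proportion of refugees might be lost at study endpoint". Potential risks says: "There are no guarantees of what participants will experience, and of the duration of changes". Expected outcomes of the study anticipates "a general improvement in mental health symptoms, psychological functioning, well-being, and economic outcomes at each assessment".

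**The concern.** A sensitivity analysis for missed visits should vary the assumption that the main model makes about the people who were not seen. LOCF instead fixes one particular assumption, that scores stop moving at the last visit. Nothing in the protocol supports that for this population. If benefit fades, early gains are carried to 12 months. If benefit lasts and baseline values are carried, it is diluted. Agreement or disagreement with the main model then says little about how far that model depends on the missing data.

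The trigger is a second problem. Loss related to outcome can hide an effect as easily as create one, so a check that runs only after a positive test looks in one direction. It is also unclear which test is meant. The condition repeats wording used for a test across scales at one follow-up, yet it follows a model fitted scale by scale over three time points. Two analysts could follow the text and run different analyses.

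**Working it through.** **Protocol figure.** With 25% versus 15%, 80% power and two-sided 0.05 (sidedness assumed), n = [1.96√(2×0.20×0.80) + 0.8416√(0.25×0.75 + 0.15×0.85)]² / 0.10² = 250 per group, which reproduces the stated 500. Going from 500 to 600 implies a loss of 100/600 = 16.7%. The protocol gives no figure for the LOCF analysis.

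**Assumed inputs (not in the protocol).** 300 per arm; unit SD; correlation 0.5 between visits; effect E = 0.3 or 0.5 SD post-intervention, E/2 at 6 months and 0 at 12 months; loss L = 16.7% or 30%, equal in both arms and random.

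**1. Fading effect.** The spurious 12-month difference is L times the average effect carried forward.

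- All loss between the post-intervention and 6-month visits: L×E, from 0.167×0.3 = 0.05 to 0.30×0.5 = 0.15 SD.
- Half the loss before the post-intervention visit, baseline carried: L×E/2 = 0.025 to 0.075 SD.
- Loss spread evenly over the three intervals: L×(0 + E + E/2)/3 = L×E/2, the same range.

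**2. Rejection of a true 12-month null.** The ANCOVA standard error is about √(2(1 − 0.5²)/300) = 0.0707 SD.

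| Bias (SD) | Bias / SE | Rejection, normal approximation | Simulated |
|---|---|---|---|
| 0.025 | 0.35 | 6.4% | 6.3% |
| 0.05 | 0.71 | 10.9% | 11.0% |
| 0.075 | 1.06 | 18.5% | 19.7% |
| 0.15 | 2.12 | 56.4% | 56.1% |

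In the same simulations (2,000-3,000 trials per setting), observed-data and likelihood analyses rejected in 4%-6%. LOCF and the likelihood analysis were both significant for SH+ in 2%-3%. They disagreed on significance in 5%-20% (half the loss early) or 10%-55% (all late).

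**3. Lasting effect of 0.25 SD, baseline carried for those never seen again.**

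- Half the loss before the post-intervention visit: 0.25×(1 − 0.083) = 0.229 and 0.25×(1 − 0.15) = 0.21 SD.
- All loss before it: 0.25×(1 − 0.167) = 0.21 and 0.25×(1 − 0.30) = 0.175 SD.
- If only post-baseline values are carried, this dilution disappears.

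**4. Other assumptions.** A second simulation used correlation 0.6 and a similar chance of loss in each interval. Bias was 0.03 SD towards SH+ for a fading 0.3 SD effect at 17%-18% loss, and 0.04 SD at about 30%. With no effect, both arms improving, and loss of about 12% versus 27%-29% (more in SH+), it was 0.05-0.08 SD against SH+. An estimate valid under missing at random stayed within about 0.01 SD of the full-data effect throughout.

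**5. The trigger.** Under full fade, a 3-df test within a scale opens in at least 96% of trials. A 6-df test across scales at 12 months opens in about 6% (between-scale correlation 0.5). With a constant effect of 0.10-0.15 SD, the within-scale trigger stays closed in 40%-74% of trials.

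**6. Informative loss that hides an effect.** If ETAU leavers alone were 0.3-0.5 SD worse than the model predicts, the main estimate would be too small by 0.167×0.3 = 0.05 to 0.30×0.5 = 0.15 SD.

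**The case against.** The strongest reply is that little depends on this analysis. LOCF is a repeat analysis of secondary scales beside a mixed ANCOVA that runs for every scale without condition. If fitted by likelihood, that model already uses the available post-baseline values under missing at random. In the simulations LOCF rarely joined the main model in a false positive (2%-3%). The covariate-adjusted models may make missing at random more plausible, and the comparison of dropout would show differential loss. All of this stands, and it limits the size of the point.

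Three stronger readings are tempting and are not supported.

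- A reader might infer that the LOCF result cannot be interpreted. It has a definite, if implausible, assumption, and the direction of its bias can be reasoned out from the visit profile.
- A reader might infer that every non-significant scale goes unchecked. That holds only if the joint test is per scale. If it is across scales, individually non-significant scales get LOCF once the test is passed, and all six go without when it is not.
- A reader might take the 56% rejection rate as expected. It needs complete fade, a 0.5 SD early effect, 30% loss and all loss after the post-intervention visit. The warning under Potential risks is addressed to participants and is not a forecast of fade; Expected outcomes anticipates benefit at each assessment.

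Imputation details and delta ranges may properly sit in an SAP. But the protocol itself names both the method and its trigger, so the objection that this is SAP detail does not remove the point.

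**Conclusion.** The point holds as a weakness in a stated rule. For whole missed assessments of the six scales, the protocol names only LOCF to 12 months and makes it depend on a significant joint test whose scope is unclear.

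Under the assumed full fade, the spurious 12-month effect is 0.025-0.075 SD with half the loss early and 0.05-0.15 SD with all of it late. Dilution of a lasting effect depends on baseline values being carried, which the text neither states nor excludes. These sizes rest on assumed trajectories, correlation and loss patterns; only the 16.7% comes from the protocol's numbers.

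On either reading of the joint test, some or all scales can go without a check for reasons unrelated to the missing data. The primary outcome is untouched, and the mixed ANCOVA is not faulted if fitted by likelihood. The change is a low-cost improvement and should be made.

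**What to change.** - Keep the mixed ANCOVA as the main scale analysis and state that it is fitted by likelihood.
- Replace LOCF with multiple imputation by arm, using the baseline, post-intervention and 6-month scores already collected, plus a prespecified delta-adjusted (tipping-point) series. Imputation under missing at random will mostly reproduce the main model; the delta series is the real test.
- Run both for every scale, whatever the significance.
- State whether the joint test is over time points within a scale or across scales at a follow-up, and what it still governs once it no longer triggers the sensitivity analysis.

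The cost is protocol or SAP wording and modest extra programming, with no new data collection. The downside is that an imputation model and a delta range have to be justified in advance.
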